Appendix 11. European LeukemiaNet Guidelines for Response in CML

Definitions of Hematologic, Cytogenetic, and Molecular Response²⁶

Response by Type	Definitions
Hematologic Complete (CHR)	WBC <10 x 10 ⁹ /L Peripheral Blood Basophils <5% No Peripheral Blood myelocytes, promyelocytes, myeloblasts in the differential Platelet count <450 x 10 ⁹ /L Spleen nonpalpable
Cytogenetic * Complete (CCyR) Partial (PCyR) Minor (mCyR) Minimal (minCyR) None (noCyR)	No Ph+ metaphases 1% to 35% Ph+ metaphases 36% to 65% Ph+ metaphases 66% to 95% Ph+ metaphases >95% Ph+ metaphases
Molecular Deep Molecular Response (MR4, MR4.5)	MR4= either (i) detectable disease with <0.01% BCR-ABL1 ^{IS} or (ii) undetectable disease in cDNA with >10 000 ABL1 transcripts MR4.5 =either (i) detectable disease with < 0.0032% BCR-ABL1 ^{IS} or (ii) undetectable disease in cDNA with >32,000 ABL1 transcripts in the same volume of cDNA used to test for BCR-ABL1.
Major (MMR)	Ratio of BCR-ABL ^{IS} ≤0.1%**.

Abbreviations: CHR, complete hematologic response; CCyR, complete cytogenetic response, PCyR, partial cytogenetic response; Ph+, Philadelphia Chromosome positive; MCyR, major cytogenetic response; mCyR, minor cytogenetic response; minCyR, minimal cytogenetic response; noCyR, no cytogenetic response; MR4, MR4.5, deep molecular response; MMR, major molecular response;.

*If bone marrow metaphases cannot be obtained or evaluated by chromosome banding analysis, the definition of CCyR (defined as <1% for FISH) may be based on interphase FISH of blood cells, provided that it is performed with Dual-Color Dual-Fusion or Dual-Fusion FISH probes and at least 200 nuclei are scored. PCyR and CCyR are counted together and reported as MCyR.

**With >=5,000 ABL1 transcripts.

Definitions of Hematologic Response for AP and BP CML^{29*}

CHR**	WBC \leq institutional upper limit of normal (ULN) ANC \geq 1.0 x 10^9 /L Platelet count \geq 100 x 10^9 /L BM Blasts \leq 5% *** No peripheral blood blasts or promyelocytes; Peripheral blood myelocytes + metamyelocytes $<$ 5%; Basophils in peripheral blood $<$ 5%* No evidence of extramedullary involvement
-------	--

*The maximum % of basophils in peripheral blood was modified from < 2 to $< 5\%$ for a less restrictive constraint and alignment with the CHR criteria for CP CML patients according to ELN guidelines.

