Second, for the set of variables collected to derive peripheral blood or bone marrow differentials at each post-baseline visit up to week 13, if a given set are still incomplete, a non-missing set of lab variables obtained ± 3 days from the scheduled visit will be utilized to complete the derivation. For visits on or after week 13, a non-missing set of lab variables obtained ± 7 days of the visit will be utilized to complete that post-baseline assessment. The last non-missing peripheral blood or bone marrow differentials collected at week 1 day 1 or up to 30 days prior to week 1 day 1 will be used for baseline assessment. For example, if the bone marrow blast count was missing, the entire non-missing bone marrow assessment, not just the blast field, from another observation will be used. Some data handling rules for data combination are specified below.

- Data combination is needed only when the full dataset is not available on a single day at a given visit. The full dataset includes peripheral blood differential for chronic phase, and both bone marrow (when available) and peripheral blood differentials for advanced phase. The extramedullary assessment when absent should not preclude the derivation, and when present should be taken into account per response criteria rules.
- During the post-baseline data combination, the latest date will be used as the date of visit and the more conservative value will be taken if there is more than one measurement for a variable. For platelet counts, in case of multiple values, the lowest value will be taken. If any value falls above or below normal range, the out-of range value will be taken.

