8.2.2. Analysis of Secondary Efficacy Endpoints

The response rate and DOR analyses are based on the evaluable analysis set for Ph+ CML patients only. The efficacy analysis is the percentage of responders cumulative anytime on-treatment or at a specific landmark, for:

- Cumulative MCyR separately for CP, AP, and BP;
- Cumulative confirmed OHR separately for AP2L, AP3L, AP4L, BP2L, BP3L, BP4L;
- Best response separately for CP, AP, and BP;
- Landmark MCyR at 3, 6, 12, 18, and 24 months separately for CP, AP, and BP;
- Landmark confirmed OHR at 3, 6, 9, 12, 18, and 24 months separately for AP and BP;
- Cumulative confirmed CHR separately for CP, AP, and BP;
- Cumulative MMR separately for CP, AP, and BP;
- Duration of CCyR separately for CP, AP, and BP;
- Duration of MMR separately for CP, AP, and BP.

Any patient not demonstrating a response on-treatment for cumulative and at the specific visit for landmark is deemed a non-responder for the respective analysis. For landmark analyses, if the patient is missing the landmark assessment however the patient is responding at the scheduled before and after visit (eg, missing Month 6/Week 26 but responding at Week 13 and Week 39, missing Month 18/Week 78 but responding at Week 52 and

Week 104, etc.), then the patient will be deemed a responder for that landmark. For cumulative MMR (including MR⁴ and MR^{4.5}) and MCyR (including CCyR), supportive analyses will be provided excluding patients with baseline response and also for patients who responded before and after initial dose reduction to 400 mg, 300 mg, and 200 mg due to an AE

The duration of cytogenetic and molecular response analyses are based on the evaluable analysis set for the subset of patients who respond for the respective endpoint. The K-M method, as described in [Section 8.1](#), will be used for estimation of the distributions of duration provided most responding patients remain on treatment until progression or loss of response. The percentages of CCyR and MMR for the respective endpoint, along with percent of censored patients still on-treatment and percent of reasons for failure will be summarized.

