Appendix 2. DEFINITIONS OF HEMATOLOGIC, CYTOGENETIC, AND MOLECULAR RESPONSE

Response by Type	Definitions
Hematologic Complete (CHR)	WBC <10 x 10⁹/L Peripheral Blood Basophils <5% No Peripheral Blood myelocytes, promyelocytes, myeloblasts in the differential Platelet count <450 x 10⁹/L Spleen nonpalpable
Cytogenetic * Complete (CCyR) Partial (PCyR) Minor (mCyR) Minimal (minCyR) None (noCyR)	No Ph+ metaphases 1% to 35% Ph+ metaphases 36% to 65% Ph+ metaphases 66% to 95% Ph+ metaphases >95% Ph+ metaphases
Molecular Deep Molecular Response (MR4, MR4.5)	MR4= either (i) detectable disease with <0.01% BCR-ABL1^{IS} or (ii) undetectable disease in cDNA with >10 000 ABL1 transcripts MR4.5 =either (i) detectable disease with < 0.0032% BCR-ABL1^{IS} or (ii) undetectable disease in cDNA with >32,000 ABL1 transcripts in the same volume of cDNA used to test for BCR-ABL1. Ratio of BCR-ABL^{IS} ≤0.1%**.
Major (MMR)	

Abbreviations: CHR, complete hematologic response; CCyR, complete cytogenetic response, PCyR, partial cytogenetic response; Ph+, Philadelphia Chromosome positive; MCyR, major cytogenetic response; mCyR, minor cytogenetic response; minCyR, minimal cytogenetic response; noCyR, no cytogenetic response; MR4, MR4.5, deep molecular response; MMR, major molecular response.

*If bone marrow metaphases cannot be obtained or evaluated by chromosome banding analysis, the definition of CCyR (defined as <1% for FISH) may be based on interphase FISH of blood cells, provided that it is performed with Dual-Color Dual-Fusion or Dual-Fusion FISH probes and at least 200 nuclei are scored.

PCyR and CCyR are counted together and reported as MCyR.

**With ≥5,000 ABL1 transcripts.

Definitions of Hematologic Response for AP and BP CML*

CHR**	WBC \leq institutional upper limit of normal (ULN) ANC \geq 1.0 x 10⁹/L Platelet count \geq 100 x 10⁹/L BM Blasts \leq 5%*** No peripheral blood blasts or promyelocytes; Peripheral blood myelocytes + metamyelocytes $<$ 5%; Basophils in peripheral blood $<$ 5%* No evidence of extramedullary involvement
--------------	---

*The maximum % of basophils in peripheral blood was modified from <2 to $<5\%$ for a less restrictive constraint and alignment with the CHR criteria for CP CML patients according to ELN guidelines.

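### The lowest-platelet rule for combined assessments is conservative for AP/BP CHR but anti-conservative for CP CHR, and its order against the out-of-range sentence is not stated

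*SAP*

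**What the plan says.** The last bullet of SAP section 7 governs post-baseline assessments assembled from more than one day. Its general principle is that "the more conservative value will be taken if there is more than one measurement for a variable". For platelets it is specific: "For platelet counts, in case of multiple values, the lowest value will be taken". The sentence after that reads "If any value falls above or below normal range, the out-of range value will be taken". None of the three distinguishes CP from AP/BP, although the bullet just before does so when it defines a full dataset. That earlier bullet also limits the scope: "Data combination is needed only when the full dataset is not available on a single day at a given visit".

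SAP Appendix 2 gives two CHR definitions. For CP the platelet criterion is "Platelet count <450 x 10⁹/L", with no lower limit. For AP and BP it is a count of at least 100 x 10^9/L, with no upper limit. Protocol Appendix 11 gives the same two criteria. SAP section 8.2.2 lists the affected analysis: "Cumulative confirmed CHR separately for CP, AP, and BP".

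**The concern.** A rule presented as conservative should never make response easier to reach. Taking the minimum does that for a lower-bound criterion (AP/BP) but works the other way for an upper-bound criterion (CP). Because the rule is not split by phase, the SAP contradicts its own principle for CP CHR.

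The out-of-range sentence adds a second difficulty. For a CP patient with one normal count and one count above 450, one sentence selects the normal value and the next selects the high one. Two programmers following the SAP could derive different CHR status from the same data. At stake are the credibility and reproducibility of a secondary response rate in a single-arm study whose estimates are read descriptively.

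**Working it through.** The plan gives no figure that depends on this rule, so there is nothing to reproduce. The check is a logic test on pairs of platelet counts (x 10^9/L).

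**Inputs.** From SAP Appendix 2: CP CHR needs a count below 450; AP/BP CHR needs at least 100. Laboratory normal limits are not in the documents. I assume a lower limit of 150 and upper limits (ULN) of 350, 400, 450 and 500.

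**Rules compared.**
- A: the lowest value always.
- B: an out-of-range value takes precedence; if both or neither are out of range, the lowest.
- C: the highest value, which is the conservative choice for an upper bound.

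**Direction.** Since min(a, b) ≤ max(a, b), whenever the highest count is below 450 so is the lowest. Rule A can therefore never turn a met CP platelet criterion into an unmet one. Every pair straddling 450 moves from not met (C) to met (A). For the AP/BP bound the same inequality means that the lowest count never favours response.

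**Example pairs.**

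| Pair | Criterion | Rule A | Rule B | Rule C |
|---|---|---|---|---|
| 300, 460 | CP <450 | 300, met | ULN 350–450: 460, not met; ULN 500: 300, met | 460, not met |
| 430, 460 | CP <450 | 430, met | ULN 350, 400, 500: 430, met; ULN 450: 460, not met | 460, not met |
| 120, 460 | CP <450 | 120, met | all four ULNs: 120, met | 460, not met |
| 90, 300 | AP/BP ≥100 | 90, not met | 90, not met | 300, met |

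The first row is where the SAP's two sentences conflict. The second (with ULN 350 or 400) and the third (with ULN 350 to 450) have both values out of range. With ULN 500, the first two rows have both values in range and the minimum decides.

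**Illustrative grid.** Take a lower value of 250 to 440 and a higher value of 450 to 600, in steps of 10: 20 x 16 = 320 pairs, all straddling 450. The share meeting the CP criterion is 100% under A and 0% under C. Under B it is:
- ULN 350: lower values 360–440 are also out of range, 9/20 = 45%.
- ULN 400: lower values 410–440, 4/20 = 20%.
- ULN 450: only pairs whose higher value is exactly 450 stay in range, 20/320 = 6.25%.
- ULN 500: higher values 450–500 are in range, 6/16 = 37.5%.

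These are shares of a uniform grid. They are not patient rates. They show that the out-of-range sentence reduces the problem without removing it, and that the remainder depends on the local ULN.

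**The case against.** The strongest reply is that the usual discordant pair, one normal count and one above 450, is already covered by the out-of-range sentence, which selects the high value unless the local ULN exceeds 450. That stands as far as it goes, but precedence is not stated and the sentence gives no choice when both values are out of range. It can also be argued that the general principle should break such ties. That is a reasonable intention, but the sentence written specifically for platelets says lowest.

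Scope is a fair objection too. For CP the full dataset is only the peripheral blood differential, and Protocol Appendix 9 places platelets and the differential in the same hematology panel, so combination should seldom be needed in CP. A favourable platelet value does not create a response alone: the white-cell, basophil, immature-cell and spleen criteria must also be met, and confirmation at least 28 days apart is required.

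A reader might go further and infer that loss of CHR is under-detected, and hence PFS biased, because loss uses a threshold of 600 or more. The documents do not support this. No duration-of-CHR endpoint is planned; duration is analysed only for CCyR, MMR, MR4 and MCyR. SAP section 6.1 takes PFS progression from the investigator's assessment, recorded as the reason for stopping treatment, and does not say it is derived from combined laboratory values.

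A reader might also conclude that CP should simply use the highest count throughout. That would create a different error. SAP Appendix 1 makes persistent platelets below 100, not related to therapy, a criterion for accelerated phase, and development of AP is the event in time to transformation for CP patients. With counts of 90 and 130, the highest value would hide that criterion.

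**Conclusion.** The point holds in a narrow form. For CP CHR the platelet sentence runs against the principle stated in the same bullet, and any error it introduces favours response. The out-of-range sentence resolves some pairs correctly, but its rank is undefined. With the minimum as tie-breaker, pairs straddling 450 still resolve towards response when both values are out of range, or when both are in range because a local ULN exceeds 450.

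It would be too strong to say that CP response is biased whenever data are combined: at least two differing counts on opposite sides of 450 are needed. The CP primary endpoint is cytogenetic and uses no platelet count. What is touched is cumulative confirmed CHR in CP and the CHR tier of best response. No effect on loss of CHR or PFS is shown.

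The size is small. It cannot be put as a change in the CP CHR rate, because the documents do not say how often combined CP assessments have discordant platelet counts. The worked examples rest on assumed laboratory limits; the one-way direction of the lowest-value rule does not.

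**What to change.** Replace the platelet sentence in SAP section 7 with a rule tied to the criterion being assessed:

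- for an upper-bound response criterion (CP CHR, below 450), use the highest platelet count;
- for a lower-bound response criterion (AP/BP CHR, at least 100), use the lowest;
- for the accelerated-phase criterion of platelets below 100, keep the lowest;
- state that, for platelets, this rule takes precedence over the out-of-range sentence.

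The cost is one or two sentences in the SAP and a small change to the derivation code. No new data are needed.

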8. STATISTICAL METHODOLOGY AND STATISTICAL ANALYSES

8.1. Statistical Methods

8.1.1. Analyses of Continuous Data

For continuous variables, the descriptive statistics include n, mean, median, standard deviation (SD), and range (minimum, maximum).

8.1.2. Analyses of Categorical Data

For categorical variables, the descriptive statistics include the count in each category, the total n, and percentage.

8.1.3. Analyses of Binary Endpoints

Exact 2-sided 95% CIs will be provided for molecular, cytogenetic, and hematologic response rates.

8.1.4. Analyses of Time-To-Event Endpoints

For time-to-event endpoints such as time to response, DOR, time to transformation, PFS, and OS, the method of analysis will either be Kaplan-Meier (K-M) or cumulative incidence of the event adjusting for the competing risk of treatment discontinuation due to any reason without the event (Gray).¹

When applying the K-M method, medians and quartiles with the associated 2-sided 95% CI will be provided. The CIs based on the Brookmeyer-Crowley log(-log) transformation method will be provided. The K-M yearly rates up through year 4 with the associated 2-sided 95% CI based on Greenwood's formula using a log(-log) transformation will also be provided.

When applying the cumulative incidence method, yearly rates up through year 4 with the associated 2-sided 95% CI based on the delta method using a log(-log) transformation will be provided.

8.2. Statistical Analyses

The efficacy endpoints will be analyzed according to the cohorts or a combination of these cohorts specified in [Section 2](#). Ph+ CML patients will be summarized separately.

8.2.1. Analysis of Primary Efficacy Endpoints

The response rate analyses are based on the evaluable analysis set for Ph+ CML patients only. The primary efficacy analysis is the percentage of responders by Week 52, done separately for:

- Confirmed MCyR for combined CP2L and CP3L;
- Confirmed MCyR for CP4L;
- Confirmed OHR separately for AP and BP.

Any patient not demonstrating a response by Week 52 is deemed a non-responder.

8.2.2. Analysis of Secondary Efficacy Endpoints

The response rate and DOR analyses are based on the evaluable analysis set for Ph+ CML patients only. The efficacy analysis is the percentage of responders cumulative anytime on-treatment or at a specific landmark, for:

- Cumulative MCyR separately for CP, AP, and BP;
- Cumulative confirmed OHR separately for AP2L, AP3L, AP4L, BP2L, BP3L, BP4L;
- Best response separately for CP, AP, and BP;
- Landmark MCyR at 3, 6, 12, 18, and 24 months separately for CP, AP, and BP;
- Landmark confirmed OHR at 3, 6, 9, 12, 18, and 24 months separately for AP and BP;
- Cumulative confirmed CHR separately for CP, AP, and BP;
- Cumulative MMR separately for CP, AP, and BP;
- Duration of CCyR separately for CP, AP, and BP;
- Duration of MMR separately for CP, AP, and BP.

Any patient not demonstrating a response on-treatment for cumulative and at the specific visit for landmark is deemed a non-responder for the respective analysis. For landmark analyses, if the patient is missing the landmark assessment however the patient is responding at the scheduled before and after visit (eg, missing Month 6/Week 26 but responding at Week 13 and Week 39, missing Month 18/Week 78 but responding at Week 52 and

Week 104, etc.), then the patient will be deemed a responder for that landmark. For cumulative MMR (including MR⁴ and MR^{4.5}) and MCyR (including CCyR), supportive analyses will be provided excluding patients with baseline response and also for patients who responded before and after initial dose reduction to 400 mg, 300 mg, and 200 mg due to an AE

The duration of cytogenetic and molecular response analyses are based on the evaluable analysis set for the subset of patients who respond for the respective endpoint. The K-M method, as described in [Section 8.1](#), will be used for estimation of the distributions of duration provided most responding patients remain on treatment until progression or loss of response. The percentages of CCyR and MMR for the respective endpoint, along with percent of censored patients still on-treatment and percent of reasons for failure will be summarized.

No COVID-19 related efficacy analyses will be performed as the primary endpoint only summarizes data up through Week 52 and all patients reached that milestone prior to the March 11, 2020 COVID-19 anchor date and for secondary endpoints, >80% of patients were already off treatment as of the anchor date. A summary of missing data before and after the anchor date will be summarized.

A listing of COVID-19 related study discontinuations will be provided.

8.2.3. Analysis of Exploratory Efficacy Endpoints

The time to molecular and cytogenetic response analyses are based on the evaluable analysis set. Cumulative incidence of response adjusting for the competing risk of treatment discontinuation due to any reason without response, as described in [Section 8.1](#), will be used. The percentage of responders without treatment discontinuation and the percentage of treatment discontinuation without response will be summarized.

The duration of cytogenetic and molecular response exploratory analyses follow the same rules as the secondary DOR analyses except the percentages of MCyR, CCyR, and PCyR and MR⁴ will be summarized.

The time to transformation analysis is based on the full analysis set. Cumulative incidence of transformation adjusting for the competing risk of treatment discontinuation due to any reason without transformation, as described in [Section 8.1](#), will be used. The percentage of transformation without treatment discontinuation and the percentage of treatment discontinuation without transformation will be summarized. The specific disease stage transformation (accelerated or blast phases) will also be listed.

The PFS analysis is based on the full analysis set. The K-M method, with or without insufficient clinical response as assessed by the investigator as an event or cumulative incidence of on-treatment progression or death adjusting for the competing risk of treatment discontinuation without the event, as described in [Section 8.1](#), will be used.

The OS analysis is based on the full analysis set. The K-M method, as described in [Section 8.1](#), will be used. The number of deaths and causes of death will be summarized. Time on study from date of first dose to date of last contact and reasons for discontinuing participation will also be summarized.

The percentage of patients with baseline and emergent mutations, along with the specific types of mutations, will be summarized. The percentage of patients with cumulative MCyR, CHR, MMR, and OHR (AP and BP patients only) by baseline mutation status will be provided. The distributions of PFS and OS will also be displayed for patients with a baseline mutation versus those assessed but without a baseline mutation.

The percentage of Ph- CML patients in each best response category will be summarized.

Missing values and incomplete data will be handled as described in [Section 7](#) of this analysis plan.

Listings for all efficacy data will also be provided.

